10.4 Analysis of Exploratory Endpoints

The following set of exploratory endpoints is planned in this study. P values are intended to be descriptive. The analysis of the exploratory endpoint will be based on the ITT population.

1. Total number of hospitalizations for coronary, cerebral, or peripheral ischemia from the time of randomization through 30 days
2. Time-to-first occurrence of CV death, MI, or stroke or severe coronary ischemia requiring urgent revascularization from the time of randomization through 90 days
3. Time to first occurrence of CV death, MI, or stroke from the time of randomization through 30 and 60 days
4. Time to first occurrence of MI by type, according to universal definition, from the time of randomization through 90 days
5. Time to occurrence of CV death from the time of randomization through 365 days
6. Time to occurrence of non-CV death from the time of randomization through 365 days

7. Total occurrence of rehospitalization for CV events and all-cause death from the time of randomization through 90 days. Rehospitalization is defined as any site-reported post-index MI hospitalization (including extension of index MI hospitalization past randomization date due to a treatment-emergent serious adverse event) that is adjudicated, regardless of adjudication outcome, or a positively adjudicated triggered event linked to a site-reported adverse event. Urgent heart failure visits with a less than 24 hour stay are not considered.
8. Total occurrence of all-cause death, MI, and stroke from the time of randomization through 90, 180 and 365 days
9. Total occurrence of CV death, MI, and stroke from the time of randomization through 90, 180, and 365 days

10. Medical resource utilization from the time of randomization through 90 days:

- a. Number of total hospitalizations
- b. Length of hospital stay
- c. Number of cardiac care unit (CCU) or intensive care unit (ICU) days
- d. Select surgeries / select procedures related to hospitalization for coronary, cerebral, or peripheral ischemia (see [Section 9.5](#) for definition)
- e. Discharge to: home with additional care, home without additional care, rehabilitation or skilled nursing facilities following hospitalization for coronary, cerebral, or peripheral ischemia

11. Change in EQ-5D-3L data from baseline to day 90

The planned analyses of the exploratory efficacy endpoints are given below in the same order as the list of endpoints above.

The hospitalizations for coronary, cerebral, or peripheral ischemia through 30 days from the time of randomization, will be analyzed similarly to the key secondary endpoint of hospitalizations through 90 days following randomizations based on a negative binomial regression model.

The exploratory time to event efficacy endpoints listed in 2 through 6 above will be analyzed in a similar manner to that of the primary endpoint. Pre-planned staged PCIs will be excluded in the analysis of the endpoint time to first occurrence of CV death, MI, stroke, or severe

coronary ischemia requiring urgent revascularization. Treatment comparison will be based on a covariate-adjusted Cox regression model for estimating the 1-sided P value, the hazard ratio and its 95% CI. The effect over time will be illustrated with a plot of the complement (1 - KM) of the Kaplan-Meier estimates. Event counts (%) will be presented.

The analysis of the total occurrence of rehospitalization (post-index MI) and all-cause death through 90 days will be based on Win Ratio methodology [Pocock et al, 2012] as described in [Section 10.2.1](#). In this analysis, clinical hierarchy is defined as all-cause death followed by hospitalization. The Win Ratio (CSL112: Placebo) will be calculated along with associated 95% CI and a 1-sided P value. A complete description of the analytical approach is given in [Appendix 15.1](#). Total occurrence of rehospitalization will also be analyzed utilizing a negative binomial model as described previously.

The exploratory endpoints including total occurrence of CV death, MI, and stroke from time of randomization through 90, 180, and 365 days and total occurrence of all-cause death, MI, and stroke from randomization through 90, 180, and 365 days will be analyzed using a negative binomial regression model in a similar manner as described in [Section 10.2.1](#) for the number of hospitalizations through 90 days.

For each exploratory endpoint based on CEC adjudicated outcomes, summary table of consistency of findings between the CEC and investigator-reported MACE will be produced as given in [Section 10.1](#). A supportive listing of individual subject data including the time to event in days and the censoring variable will be presented.

The relationship between medical resource utilization and treatment with CSL112 will be descriptively summarized. The endpoints of medical resource utilization including the number of hospitalizations, length of hospital stay (days), CCU or ICU stay (days) and number of select surgeries/select procedures related to hospitalization for coronary, cerebral, or peripheral ischemia will be treated as count data for the purpose of analysis. For each subject, total counts either in number of admissions or duration of stay will be derived across all hospitalizations occurring during the 90 day period from randomization. The analyses of these endpoints will use a negative binomial regression model as described for the key secondary endpoint of CV hospitalizations described in [Section 10.2.1](#). Discharge to following CV hospitalization will be descriptively summarized with counts and percentages in each category by treatment arm.

The EQ-5D-3L is a patient self-assessment of five dimensions of health-related quality of life: mobility, self-care, usual activities, pain or discomfort and anxiety or depression. Each dimension is measured on a 3-point scale where a higher score corresponds to a worse health state. Scores from the individual dimensions will be used to calculate an overall utility score for each patient using the algorithm specified by the developers of the instrument [[EuroQoL, 2015](#)]. The EQ VAS is a continuous 100 point integer scale from 0 (the worst health you can imagine) to 100 (the best health you can imagine). Further details can be found in [Appendix 15.2](#).

Response to each of the five dimensions will be descriptively summarized. For each dimension and treatment, shift tables will be employed indicating the number of subjects whose response falls into a grid defined by the baseline value on one axis and the post-treatment value on the other axis. To compare treatments on each dimension, the number (%) of subjects with improvement, no change, or worsening from baseline to the post-treatment value will be analyzed using a chi-square test for a 2 x 3 contingency table with ordered categories of response.

Both the utility score and the EQ VAS are continuous response variables describing the patient's self-assessment of their health status at baseline and post-treatment. Descriptive statistics including the mean, median, SD, minimum and maximum will be provided at baseline, post-treatment and for the change from baseline. The change from baseline will be compared between treatments employing an analysis of variance model (ANOVA) including terms for treatment, region, type of index MI (STEMI vs NSTEMI), management of index MI (PCI vs. medical management), age (as a continuous variable), diabetes, peripheral artery disease, prior history of MI, and a term for interaction between index MI type and index MI management.

Additional Exploratory Efficacy Endpoints

The following additional exploratory efficacy endpoints will be analyzed based on the ITT population. Endpoints consisting of other time points (90, 180, or 365 days) not explicitly listed in this document will also be analyzed.

1. Time-to-occurrence of all-cause death from the time of randomization through 90, 180 days and end of study

2. Time to occurrence of non-COVID-19 related death from the time of randomization through day 365. All deaths resulting from COVID-19 will be censored in this analysis
3. Time-to-first occurrence of CV death or MI from the time of randomization through 90 days
4. Time to first occurrence of CV death, MI, or stroke from the time of randomization through the end of study
5. Time-to-first occurrence of all-cause death, MI, or stroke from the time of randomization through 90 days
6. Time to occurrence of CV death from the time of randomization through 180 days and end of study
7. Time-to-first occurrence of MI from the time of randomization through 180, 365 days and end of study
8. Time-to-first occurrence of stroke from the time of randomization through 180, 365 days and end of study
9. Time to occurrence of thrombotic (ischemic) strokes with hemorrhagic conversion from the time of randomization through day 365
10. Time to occurrence of hemorrhagic stroke from the time of randomization through day 365
11. Time-to-first occurrence of stroke including sub-arachnoid stroke from the time of randomization through days 90, 180 and 365
12. Medical resource utilization from the time of randomization through 180 and 365 days:
 - a. Number of total hospitalizations
 - b. Length of hospital stay
 - c. Number of cardiac care unit (CCU) or intensive care unit (ICU) days
 - d. Select surgeries/select procedures related to hospitalization for coronary, cerebral, or peripheral ischemia

e. Discharge to: home with additional care, home without additional care, rehabilitation or skilled nursing facilities following hospitalization for coronary, cerebral, or peripheral ischemia

13. Assessment of neurological disability using the Modified Rankin Score

The time to event endpoints in 1 through 11 will be analyzed similarly to the primary endpoint (see [Section 10.1](#)) while endpoints listed in 12a through 12d will be analyzed using a similar approach described in [Section 10.2.1](#) for the analysis of total number of hospitalizations for coronary, cerebral, or peripheral ischemia. The endpoint 12e will be descriptively summarized with counts and percentages of subjects in each category. The endpoint listed in 13 utilizes a rating scale of neurological disability ranging from 0 to 6, with 0 = total lack of symptoms, 1 = no significant disability, 2 = slight disability, 3 = moderate disability, 4 = moderately severe disability, 5 = severe disability, and 6 = death. Subjects experiencing stroke during the course of the study will be graded to reflect the extent of neurological dysfunction. Descriptive summaries will be generated as follows: counts and % of subjects each level and also as a collapsed value (0-2; not disabling) vs. (3-6; disabling).

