### **2.3.2                   Exploratory Endpoints**

The endpoints for evaluation of the exploratory objectives are:

1. Total number of hospitalizations for coronary, cerebral, or peripheral ischemia from the time of randomization through 30 days.
2. Time to first occurrence of CV death, MI, stroke, or severe coronary ischemia requiring urgent revascularization from the time of randomization through 90 days.
3. Time to first occurrence of CV death, MI, or stroke from the time of randomization through 30 and 60 days.
4. Time to first occurrence of MI by type, according to the universal definition, from the time of randomization through 90 days.
5. Time to occurrence of CV death from the time of randomization through 365 days.
6. Time to occurrence of non-CV death from the time of randomization through 365 days.
7. Total occurrence of re-hospitalization for CV events and all-cause death from the time of randomization through 90 days.
8. Total occurrence of CV death, MI, and stroke from the time of randomization through 90, 180, and 365 days.
9. Total occurrence of all-cause death, MI, and stroke from the time of randomization through 90, 180, and 365 days.
10. Medical resource utilization from the time of randomization through 90 days:
  - a. Number of total hospitalizations.
  - b. Length of hospital stay.
  - c. Number of critical care unit (CCU) or intensive care unit (ICU) days.
  - d. Select procedures / surgeries related to hospitalization for coronary, cerebral, or peripheral ischemia.

- e. Discharge status to home with or without additional care, rehabilitation, and skilled nursing facilities following hospitalization for coronary, cerebral, or peripheral ischemia.
11. Change in EQ-5D-3L data from baseline to Day 90.
12. Pharmacokinetic endpoints will include the following:
  - a. Baseline-corrected plasma apoA-I concentrations.
  - b. Baseline-corrected plasma PC concentrations.
  - c. Concentration in plasma at end-of infusion for apoA-I and PC.
  - d. Accumulation ratio for apoA-I and PC.
13. Pharmacodynamic endpoints include the following:
  - a. Total cholesterol efflux.
  - b. ABCA1-dependent efflux.
  - c. ABCA1-independent efflux.

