### **3.7.4 Clinical Events Committee**

An independent Clinical Events Committee (CEC) will review and adjudicate each suspected CV event endpoint while blinded to treatment assignments. Suspected CV event endpoints include all-cause mortality, CV death, all MI, all stroke, and hospitalizations for coronary, cerebral, or peripheral ischemia (including coronary revascularization). The CEC will also review and adjudicate the occurrence of potential hepatic injury, including results from

hepatic laboratory tests and hepatic injury assessments, and new or worsening heart failure (HF), in a blinded fashion. A common group of qualified scientists and physicians will prepare the definitions of endpoints and instructions for interpretation based on available guidance. The CEC is described in further detail in its charter.

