9.5 Prior and Concomitant Procedures

The number (%) of subjects undergoing a PCI for the index MI will be summarized based on the ITT Analysis Set. Additional coronary revascularizations planned at the time of index MI (ie, staged PCIs) will be summarized as occurring before or after randomization. Planned procedures which are performed after randomization and adjudicated by the CEC will be identified based on the procedure type and adjudication outcome (procedure type = PCI, procedure date is after randomization date, adjudication criteria are not met, or criteria are met and adjudicated as an elective, staged procedure). All coronary revascularization procedures occurring post-randomization will be adjudicated by the CEC. The number (%) of subjects undergoing coronary revascularization will be summarized as adjudicated through 90 days, and 365 days. This table will include the total number of procedures undergone by study subjects. In each period, the type of procedure as well as elective (staged, non-staged, or unplanned) or urgent nature of the procedure will be summarized. Procedures not reported by investigator but identified during back end review of study data and triggered for adjudication will be included.

All investigator-reported procedures for cerebral or peripheral ischemia reported on or after randomization through study Day 90, Day 91-180, and Day 181-365 will be summarized using the ITT Analysis Set and will present the number (%) of subjects undergoing a procedure by type and treatment group.

Supporting listing of individual subject data will be generated for prior and concomitant procedures.

The exploratory endpoint, select surgeries and procedures related to hospitalization for coronary, cerebral, or peripheral ischemia will consider all revascularization procedures occurring during a positively-adjudicated hospitalization for ischemia. This analysis will count procedures with dates contained within admission and discharge dates as reported by investigator or within 10 days following admission date if the discharge date is not available. Positive adjudication of triggered coronary revascularization procedures will also be included based on the CEC-reported procedure date.

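### SAP endpoint 7 (rehospitalization for CV events) does not exclude admissions for pre-planned staged PCI, so they would count as CV rehospitalizations

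*SAP*

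**What the plan says.** Protocol 2.3.2 lists exploratory endpoint 7 as "Total occurrence of re-hospitalization for CV events and all-cause death from the time of randomization through 90 days". The protocol does not say what makes a rehospitalization one for CV events.

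SAP 10.4 supplies the operational rule: "Rehospitalization is defined as any site-reported post-index MI hospitalization" "that is adjudicated, regardless of adjudication outcome, or a positively adjudicated triggered event linked to a site-reported adverse event". An extension of the index stay counts only if a treatment-emergent SAE caused it. One type of visit is excluded by name: "Urgent heart failure visits with a less than 24 hour stay are not considered". The modification history lists clarification of this endpoint's derivation among the version 4.0 changes, so the wording is deliberate.

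Three other places decide what falls under the rule:

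- SAP 9.5: "All coronary revascularization procedures occurring post-randomization will be adjudicated by the CEC". Planned procedures done after randomization are then recognised by their verdict: "adjudication criteria are not met, or criteria are met and adjudicated as an elective, staged procedure".
- SAP 10.4, for endpoint 2: "Pre-planned staged PCIs will be excluded in the analysis of the endpoint time to first occurrence of CV death, MI, stroke, or severe" coronary ischemia leading to urgent revascularization. No such sentence is written for endpoint 7.
- Protocol 3.7.4 places coronary revascularization within the ischemic-hospitalization events that the committee reviews, and adds: "The CEC will also review and adjudicate the occurrence of potential hepatic injury".

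Endpoint 7 is analysed by win ratio and by negative binomial regression. For the win ratio, SAP 10.4 points to Appendix 15.1 as the complete description.

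**The concern.** The rule takes the fact that an admission was adjudicated as the sign that it was for a CV event. That fails for staged PCI. The decision to do the procedure was made at the index MI, before randomization, so the admission is neither a new CV event nor an outcome that four weekly infusions could be expected to prevent. It is still adjudicated, so it is counted.

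The SAP's authors saw the same problem for endpoint 2 and removed pre-planned staged PCI there. Without a matching sentence, endpoint 7 would be reported under a CV-events label while including planned procedures. If treatment does not affect those admissions, they move the rate ratio and the win ratio toward 1.

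A lesser point of wording is that the rule does not limit adjudication to CV event types. Read literally, it could take in an admission sent to the committee for potential hepatic injury.

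**Working it through.** **Tracing a staged-PCI admission through the rules**

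1. A subject's index MI plan includes a second PCI. The subject is randomized, discharged and readmitted within 90 days for it.
2. The site reports the hospitalization. It is post-index and not an extension of the index stay, so it meets the base condition in SAP 10.4.
3. The procedure is a coronary revascularization after randomization, so it is adjudicated (SAP 9.5; Protocol 3.7.4).
4. The verdict is either that criteria are not met, or that they are met and the procedure is elective and staged (SAP 9.5). Endpoint 7 accepts any verdict for a site-reported admission, so both count.
5. The heart failure exclusion does not apply, and the staged-PCI exclusion is limited to endpoint 2. The admission scores one CV rehospitalization.

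Staged PCIs completed before randomization fall outside the endpoint. Those done during an extended index stay count only if a treatment-emergent SAE caused the extension.

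**How common this is**

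The documents give no count. They give no reason to presume it is rare: multivessel disease is required (Protocol 4.1.1, criterion 5), and planned staged PCI is both a coded baseline variable (SAP 8.2.9) and a prespecified subgroup (SAP 10.1.2).

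**Size, as an illustration only**

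No figure in the plan depends on this definition, so there is nothing to reproduce. The assumptions are:

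- a rate ratio of 0.80 on the remaining admissions, borrowed from the hazard ratio hypothesised for the primary endpoint;
- a share f of counted placebo admissions that treatment does not affect, at the same rate in both arms.

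Observed rate ratio = (1 − f) × 0.80 + f × 1.

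| f | Calculation | Observed ratio |
|---|---|---|
| 10% | 0.72 + 0.10 | 0.82 |
| 20% | 0.64 + 0.20 | 0.84 |
| 30% | 0.56 + 0.30 | 0.86 |
| 40% | 0.48 + 0.40 | 0.88 |
| 50% | 0.40 + 0.50 | 0.90 |

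The distance from 1 shrinks by the fraction f. The win ratio was not computed. Death is compared first there, so extra admissions matter only in pairs that death does not decide.

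**Appendix 15.1**

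The appendix describes its composite as ischemic hospitalizations (coronary, cerebral, peripheral) or all-cause death. That fits the sensitivity analysis of the key secondary endpoint in SAP 10.2.1. It is not the set defined for endpoint 7 in SAP 10.4, although 10.4 relies on it.

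**The case against.** The case for leaving the text alone has several parts.

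- **A broader tier may be intended.** The key secondary endpoint already counts only admissions that meet committee criteria over the same 90 days (SAP 10.2.1), and endpoint 10a counts all site-reported hospitalizations. Endpoint 7 can reasonably sit between them. The protocol leaves its CV-events wording undefined, so the SAP does not contradict it. This stands.
- **A negative verdict does not mean non-CV.** A reader might infer that every negatively adjudicated admission is wrongly counted. The documents do not support that. Under Protocol 9.6.4 and 9.6.5, a negative verdict means only that the charter's endpoint criteria were not met. A cardiac admission can miss them, and the charter is not among the documents.
- **The different rule for triggered events can be explained.** A reader might see an inconsistency because triggered events need a positive verdict and site-reported ones do not. SAP 10.1 says trigger terms come from sponsor review and not from the investigator. The rule can be read as counting an admission that either the site or the committee treated as an endpoint event.
- **The hepatic case is weak.** A reader might infer that liver admissions will be reported as CV failures. The committee adjudicates the hepatic event for safety, not the admission, and the endpoint's name still says CV events. The wording leaves the case open, but it was probably not intended.
- **Procedures versus admissions.** SAP 9.5 speaks of adjudicated procedures and SAP 10.4 of adjudicated hospitalizations, and the link between them in the data is not visible. This is a fair caution, but Protocol 3.7.4 treats coronary revascularization as part of the ischemic-hospitalization events under review.

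None of this supplies the missing staged-PCI exclusion.

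**Conclusion.** The concern holds for staged PCI. As written, post-randomization admissions for a PCI planned at the index MI count as CV rehospitalizations in both analyses of endpoint 7, and nothing elsewhere in the protocol or SAP removes them. The likely direction is toward no effect, provided treatment does not affect these admissions and they are balanced between arms. The size is unknown; the range of 0.82 to 0.90 rests wholly on assumed inputs and is not a prediction.

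The hepatic point is one of wording only. If such admissions were counted and treatment affected their frequency, the shift could go either way. Counting admissions whatever the verdict is a defensible choice for other suspected CV events.

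The consequence is limited. The endpoint is exploratory, its P values are descriptive (SAP 10.4), it lies outside the gatekeeping procedure (SAP 7.4), and no primary or key secondary test depends on it.

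**What to change.** In the endpoint 7 definition in SAP 10.4:

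1. Exclude admissions whose only adjudicated event is an elective, pre-planned staged PCI, in line with endpoint 2.
2. State that adjudicated means adjudicated as a suspected CV event, so that potential hepatic injury does not qualify.
3. Keep the any-verdict rule for other suspected CV admissions if the broader tier is intended.
4. Add a sensitivity analysis restricted to positively adjudicated CV admissions, including heart failure.
5. Align Appendix 15.1 with the endpoint 7 definition, or state which hospitalizations enter each of the two win ratio analyses.

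The cost is SAP wording and one extra analysis. The adjudication verdicts and the planned staged PCI variable are already part of the planned data. The downside is slightly fewer counted events.
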